8.2 VISIT 1 – SCREENING

This screening visit must occur within the preceding 42 days of initiating study therapy. However, screening lab tests taken as part of standard of care with 84 days of study baseline (visit 2) can be used to assess eligibility.

- Signed informed consent prior to any study related procedures,
- Demographics
- Medical History
- Document HIV history including date of diagnosis, antiretroviral therapy and HIVRNA results
- Complete physical examination, including height and weight. After the participant signs consent, any new events/findings not present in the participant's medical history or is a worsening side effect should be recorded as adverse events in the eCRF.

- Vital signs (heart rate, blood pressure, respirations and temperature).
- A detailed questionnaire regarding past and current alcohol exposure will be obtained (the AUDIT questionnaire will be used, as this is a well validated measurement for quantifying alcohol exposure) [appendix 1].
- Concomitant medication with indication.
- Document current adverse events
- Haematology analysis (haemoglobin, haematocrit, platelet count, white blood cell count including differential count)
- Serum chemistry analysis (sodium, potassium, chloride, creatinine, eGFR, bicarbonate, total protein, albumin, ALT, AST, ALP, total bilirubin), hsCRP
- Women of childbearing potential: serum pregnancy test
- Hepatitis C antibody test and if positive HCV RNA screening, to be performed if not tested within the last 3 months as part of SOC
- Hepatitis B surface antigen test – only to be performed if not tested within the last 3 months as part of SOC
- CD4+ and CD8+ T-cell count
- Plasma HIV RNA (clinical assay) – only to be performed if not part of standard of care tests within the preceding 3 months of anticipated Day 1 of treatment.

An additional [REDACTED] of blood will be collected for study specific tests which include:

- Plasma HIV RNA (single copy assay)
- CA-US RNA on CD4+ T cells
- Cell associated HIV DNA (total and integrated) in CD4+ cells
- p24 expression
- PBMC and plasma storage
- Plasma storage for measuring disulfiram levels (control)
- Serum storage for measuring vorinostat levels (control)

8.3 VISIT 2 - BASELINE

This baseline visit will occur on the day of initiating study therapy **AND** prior to the first disulfiram dose.

- Eligibility will be reconfirmed
- Medical history ascertained
- Clinical review including vital signs
- Review of current concomitant medications since last visit
- Review of current adverse events since last visit
- 6mL blood test for plasma HIV RNA (clinical assay)

An additional [REDACTED] of blood will be collected for study specific tests which include:

- Plasma HIV RNA (single copy assay)
- CA-US RNA on CD4+ T cells
- Cell associated HIV DNA (total and integrated) in CD4+ cells
- p24 expression
- TILDA assay
- PBMC and plasma storage

- Collection of plasma for disulfiram and vorinostat concentrations
- PAX gene tube for storage and future genetic studies
- Plasma storage for measuring disulfiram pK levels (control)
- Serum storage for measuring vorinostat pK level (control)

8.4 VISIT 3 – DAY 8

This visit and procedures will occur prior to both disulfiram **AND** vorinostat dosing.

- Clinical review including vital signs
- Review of current concomitant medications since last visit
- Review of current adverse events since last visit
- Haematology and serum chemistry analysis

An additional [REDACTED] of blood will be collected for study specific tests which include:

- Plasma HIV RNA (single copy assay)
- CA-US RNA on CD4+ T cells
- p24 expression
- PBMC and plasma storage
- Collection of plasma for measuring disulfiram pK levels
- Collection of serum for measuring vorinostat pK levels (control in the presence of disulfiram)
- PAX gene tube for storage and future genetic studies

8.5 VISIT 4 – DAY 11

This visit and procedures will occur 24 hours after day 10 vorinostat dosing **AND** before day 11 disulfiram dosing.

- Vital signs
- Review of current concomitant medications since last visit
- Review of current adverse events since last visit
- Haematology and serum chemistry analysis

An additional [REDACTED] of blood will be collected for study specific tests which include:

- Plasma HIV RNA (single copy assay)
- CA-US RNA on CD4+ T cells
- p24 expression
- PBMC and plasma storage
- Collection of plasma for measuring disulfiram pK levels
- Collection of serum for measuring vorinostat pK levels
- PAX gene tube for storage and future genetic studies

8.6 VISIT 5 – DAY 22

This visit and procedures will occur prior to both disulfiram **AND** Vorinostat dosing.

- Clinical review including vital signs
- Review of current concomitant medications since last visit
- Review of current adverse events since last visit

- Haematology and serum chemistry analysis

An additional [REDACTED] of blood will be collected for study specific tests which include:

- Plasma HIV RNA (single copy assay)
- CA-US RNA on CD4+ T cells
- p24 expression
- PBMC and plasma storage
- Collection of plasma for measuring disulfiram pK levels
- Collection of serum for measuring vorinostat pK levels

8.7 VISIT 6 – DAY 25

This visit and procedures will occur 24 hours after day 24 vorinostat dosing **AND** before day 25 disulfiram dosing.

- Vital signs
- Review of current concomitant medications since last visit
- Review of current adverse events since last visit
- CD4+ and CD8+ counts

An additional [REDACTED] of blood will be collected for study specific tests which include:

- Plasma HIV RNA (single copy assay)
- CA-US RNA on CD4+ T cells
- p24 expression
- PBMC and plasma storage
- Collection of plasma for measuring disulfiram pK levels
- Collection of serum for measuring vorinostat pK levels
- PAX gene tube for storage and future genetic studies

8.8 VISIT 7 – END OF TREATMENT

This visit and procedures will occur after the last disulfiram dosing, day 28.

- Clinical review including vital signs
- Review of current concomitant medications since last visit
- Review of current adverse events since last visit
- Haematology analysis (haemoglobin, haematocrit, platelet count, white blood cell count including differential count)
- Serum chemistry analysis (sodium, potassium, chloride, creatinine, eGFR, bicarbonate, total protein, albumin, ALT, AST, ALP, total bilirubin), hsCRP
- 6mL blood test for plasma HIV RNA (clinical assay)

An additional [REDACTED] of blood will be collected for study specific tests which include:

- Plasma HIV RNA (single copy assay)
- CA-US RNA on CD4+ T cells
- p24 expression
- PBMC and plasma storage
- Collection of plasma for measuring disulfiram pK levels
- Collection of serum for measuring vorinostat pK levels

8.9 VISIT 8 – SAFETY VISIT

The visit and procedures will occur on day 56 ± 7 days. This is 28 days after the last disulfiram dose.

- Vital signs
- Review of current concomitant medications since last visit
- Review of current adverse events since last visit
- CD4+ and CD8+ counts

An additional [REDACTED] of blood will be collected for study specific tests which include:

- Plasma HIV RNA (single copy assay)
- CA-US RNA on CD4+ T cells
- Cell associated HIV DNA (total and integrated) in CD4+ cells
- p24 expression
- TILDA assay
- PBMC and plasma storage
- Collection of plasma for measuring disulfiram pK levels
- Collection of serum for measuring vorinostat pK levels

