5.2 STUDY DESIGN

This is a single arm, dual site, clinical trial in HIV-infected patients on suppressive ART with a before-after design (figure 1). Targeted enrolment is 15 study participants. All enrolled study participants will receive treatment with

- Disulfiram 2000mg once daily for 28 days (days 1 - 28), plus
- Vorinostat (400mg, once daily) given on days 8, 9 10 and 22, 23 and 24. Total of 6 days.

The duration of study therapy is 28 days.

Figure 1. Study design and sampling schedule

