8. STUDY PROCEDURES

8.1 SCHEDULE OF ACTIVITIES

A total of 9 visits including one screening and one baseline visit will be performed during the study. All study visits will occur in the morning and the time of visits will always be recorded. A full schedule of activities is provided below:

Table 1: Schedule of assessments

Visit #	1 screening	2 baseline	3	4	5	6	7 EOT	8	9 EOS
Days relative to starting study therapy	-42 to 0 days pre-study therapy	1 pre-study therapy	8	11	22	25	28	56 ± 7	196 ± 10
Study activities									
Informed consent	X								
Medical history (incl/excl criteria)	X	X							
Vital signs (includes weight)	X (+ height for this visit only)	X	X	X	X	X	X	X	X
Clinical review	X (+ physical examination for this visit only)	X	X	X	X	X	X		X
Alcohol Questionnaire	X								
Concomitant medication review	X	X	X	X	X	X	X	X	X
Adverse event review	X	X	X	X	X	X	X	X	X
Study drug administration - Disulfiram		X Day 0 - 28							
Study drug administration - Vorinostat			X Days 8 - 10		X Days 22 - 24				
Pathology									
Haematology (FBE)	X		X	X	X		X		X
Clinical biochemistry (renal function, liver enzymes, electrolytes)	X		X	X	X		X		X
Pregnancy test (WOCBP only)	X								

Visit #	1 screening	2 baseline	3	4	5	6	7 EOT	8	9 EOS
Days relative to starting study therapy	-42 to 0 days pre-study therapy	1 pre-study therapy	8	11	22	25	28	56 ± 7	196 ± 10
Hep C Ab and HBsAg	X								
CD4 and CD8 counts	X					X		X	
Plasma HIV RNA (commercial assay)	X*						X		
Study Specific Specimens									
Plasma HIV RNA (SCA)	X	X	X	X	X	X	X	X	X
CA-US HIV RNA	X	X	X	X	X	X	X	X	X
p24 expression	X	X	X	X	X	X	X	X	X
HIV DNA	X	X						X	X
TILDA		X						X	
Plasma vorinostat and disulfiram		X	X	X	X	X	X	X	X
Plasma and PBMC storage	X	X	X	X	X	X	X	X	X
PAX gene tube		X	X	X		X			X
Blood Tubes required									
ACD Tubes (10 mL)	█	█	█	█	█	█	█	█	█
SST Tube (3.5 mL)	█	█	█	█	█	█	█	█	█
K2EDTA Tube (4 mL)	█	█	█	█	█	█	█	█	█
PAXgene tube (3 mL)	█	█	█	█	█	█	█	█	█
Total volume (mL)	█	█	█	█	█	█	█	█	█

* - only to be performed if the test was not ordered as part of standard of care in the previous 3 months.

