8.10 VISIT 9 – END OF STUDY

The visit and procedures will occur 6 months (168 days) after the last disulfiram dose.

- Vital signs
- Review of current concomitant medications since last visit
- Review of current adverse events since last visit
- Haematology analysis (haemoglobin, haematocrit, platelet count, white blood cell count including differential count)
- Serum chemistry analysis (sodium, potassium, chloride, creatinine, eGFR, bicarbonate, total protein, albumin, ALT, AST, ALP, total bilirubin), hsCRP
- CD4+ and CD8+ counts

An additional [REDACTED] of blood will be collected for study specific tests which include:

- Plasma HIV RNA (single copy assay)
- CA-US RNA on CD4+ T cells
- Cell associated HIV DNA (total and integrated) in CD4+ cells
- p24 expression
- PBMC and plasma storage
- Collection of plasma for measuring disulfiram pK levels
- Collection of serum for measuring vorinostat pK levels
- PAX gene tube for storage and future genetic studies

The total study specific blood volume collected for a participant over the 9 visits (approximately 6 months) will be 602.5 mL.

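### The Day 56 safety visit has no serum chemistry, so participants who complete disulfiram have no scheduled liver tests off the drug until Day 196

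*Combined protocol and SAP*

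**What the plan says.** Section 8.9, headed "VISIT 8 – SAFETY VISIT", places Visit 8 at Day 56 ± 7 and says "This is 28 days after the last disulfiram dose". Its clinical items are vital signs, concomitant medication review, adverse event review and CD4/CD8 counts. It then says that additional "blood will be collected for study specific tests which include" several virological assays, storage samples, and plasma and serum for drug levels. No haematology or chemistry appears.

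Table 1 (Section 8.1) agrees. The row beginning "Clinical biochemistry (renal function, liver enzymes, electrolytes" is marked at Visits 1, 3, 4, 5, 7 and 9 and blank at Visits 2, 6 and 8. The haematology row has the same pattern. Clinical review is also blank at Visit 8, and at no other visit.

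On either side of Visit 8:

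- Section 8.8 (Visit 7): "This visit and procedures will occur after the last disulfiram dosing, day 28". Haematology and serum chemistry are included.
- Section 8.10 (Visit 9): "The visit and procedures will occur 6 months (168 days) after the last disulfiram dose". Both panels are included again.

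Section 5.2 gives the second drug's timing: "Vorinostat (400mg, once daily) given on days 8, 9 10 and 22, 23 and 24".

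Under Section 6.5, anyone who stops study drug early is asked back one week later for safety monitoring, and then for the final visit. The laboratory content of the one-week visit is not stated, and Visit 8 is not part of this modified follow-up.

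**The concern.** A visit named for safety, four weeks after dosing ends and with blood already being drawn, carries no liver or renal chemistry. The Day 28 sample is an end-of-treatment value, because it is taken on the day of the last dose. A participant who completes treatment then has no scheduled chemistry until the final visit.

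Tolerability is a primary objective (Section 4.2.2), and Section 13.4 says safety will be monitored at study visits as set out in Sections 8 and 10, so the schedule itself carries that commitment. Section 3.3 names hepatitis as the main safety worry with disulfiram. The regimen also gives far more disulfiram in total than either of the two HIV studies the protocol relies on. What is at stake is an asymptomatic rise in liver enzymes after treatment ends, which nobody would be prompted to look for.

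**Working it through.** **Inputs.** Last disulfiram dose on Day 28 (Sections 5.2 and 8.8). Visit 8 on Day 56 ± 7 and Visit 9 on Day 196 ± 10 (Table 1). Vorinostat courses end on Days 10 and 24 (Section 5.2). Post-baseline panels on Days 8, 11, 22, 28 and 196 (Table 1). Earlier disulfiram exposure and the fatal hepatitis rate from Section 3.3.

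**1. Reproduce the plan's intervals.** Last dose to Visit 9: 196 − 28 = 168 days, as Section 8.10 states. Last dose to Visit 8: 56 − 28 = 28 days, as Section 8.9 states.

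**2. Last disulfiram dose to the first scheduled off-drug chemistry, for completers.**

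- As written: 168 days. With the Visit 9 window: 186 − 28 = 158 to 206 − 28 = 178.
- With chemistry at Visit 8: 28 days. With the Visit 8 window: 49 − 28 = 21 to 63 − 28 = 35.
- Interval left between Visits 8 and 9: 196 − 56 = 140 days (186 − 63 = 123 to 206 − 49 = 157).

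**3. Vorinostat coverage.** After the first course, panels fall at 11 − 10 = 1 day and 22 − 10 = 12 days. After the second, the Day 28 panel falls at 28 − 24 = 4 days. The gap therefore concerns disulfiram.

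**4. Total disulfiram exposure.** This trial: 28 × 2 g = 56 g. The cited HIV studies: 14 × 0.5 g = 7 g, and at most 3 × 2 g = 6 g. Section 3.3 also reports older use in alcoholism at 1 to 3 g and up to 6 g as broadly safe, but gives no duration, so total exposure there cannot be compared.

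**5. Is fatal hepatitis the expected yield?** At 1 per 25,000 patients treated per year, 15 participants for a full year give 15/25,000 = 0.06%. For 28 days of treatment, 15 × 28/365 = 1.15 patient-years, and 1.15/25,000 = 0.0046%. It is not.

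**6. What other provisions would already catch.** Symptomatic events are picked up at the adverse event review. Recorded events are followed to resolution or stabilisation (Section 10.2). Testing to follow up abnormal findings is free to participants (Section 13.4). Persistent changes show at Day 196. What is left is a new, asymptomatic abnormality that begins after Day 28 and has gone by Day 196.

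**7. Blood volume.** Tube counts are redacted. Assuming one 3.5 mL SST tube, the addition is 3.5/602.5 = 0.6% of the stated study volume. With one 4 mL K2EDTA tube for haematology as well, it is 7.5/602.5 = 1.2%.

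**The case against.** The strongest reply is that this is a preference. No document requires a Day 56 panel, and Section 8.9 and Table 1 agree with each other. A reader might infer a contradiction from the visit's name, but the documents do not support that: the content is consistent in both places.

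Several parts of the reply narrow the point, and they stand:

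- **Early stoppers.** A reader might infer that nobody has a safety contact off the drug before Day 56. Section 6.5 shows otherwise for those who stop early, although the laboratory content of that contact is unspecified. Since Visit 8 is outside their follow-up, a panel there would not reach them. The gap and the benefit belong to completers.
- **Haematology.** A reader might extend the point to blood counts. The documents give no disulfiram reason for that. The blood-count toxicity they describe is vorinostat's (Section 13.4.2), and the Day 28 panel covers it.
- **Neurotoxicity.** Section 11.3 refers to observed neurotoxicity. A chemistry panel would not have detected it.
- **Effect on the tolerability results.** Under Section 10.1.1, an asymptomatic change found at Day 56 becomes an adverse event only if it needs further testing or intervention, or if the investigator judges it one. Few would enter the summary.
- **Timing.** Sections 9.12 and 11.3 refer to findings already observed in the trial, so the number still to reach Visit 8 could be small or zero.

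One part does not stand. Following known events to resolution, with free follow-up testing, cannot reveal an abnormality that nobody has measured.

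**Conclusion.** The point holds as a small, optional improvement to safety monitoring. Participants who complete disulfiram have no scheduled liver chemistry for 168 days (158 to 178) after the last dose, and a panel at Visit 8 would shorten that to 28 days (21 to 35). The intervals follow directly from the schedule.

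How often the panel would find something cannot be estimated. The documents give no rate, onset or duration for asymptomatic enzyme changes after disulfiram stops, so a reader should not infer any particular chance of detection. Nor would a Day 56 laboratory estimate follow, because the plan summarises adverse events and not laboratory prevalence by visit. Changes that resolve before Day 56, or that arise and resolve between Visits 8 and 9, would still be missed. The primary endpoint, the power and the planned analyses are untouched.

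**What to change.** In Section 8.9 and Table 1, add to Visit 8 the serum chemistry panel already listed for Visits 7 and 9 (including ALT, AST, ALP, total bilirubin and creatinine), drawn at the existing venepuncture, for participants who have not yet reached that visit. Haematology may be added for convenience but is not needed for this purpose. Abnormalities meeting Section 10.1.1 enter the adverse event summary already planned. A clinically relevant Day 28 result should still be rechecked promptly under Section 10.2 and not held over to Day 56.

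The cost is a minor amendment and at most 15 panels, fewer with early stoppers or participants already past Visit 8. The extra blood is about 3.5 mL each, or 7.5 mL with haematology, under the tube assumption above. Some incidental mild abnormalities will need follow-up. No new visit or analysis is required. If no participant is still to reach Visit 8, there is nothing to change.

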8.10 VISIT 9 – END OF STUDY

The visit and procedures will occur 6 months (168 days) after the last disulfiram dose.

- Vital signs
- Review of current concomitant medications since last visit
- Review of current adverse events since last visit
- Haematology analysis (haemoglobin, haematocrit, platelet count, white blood cell count including differential count)
- Serum chemistry analysis (sodium, potassium, chloride, creatinine, eGFR, bicarbonate, total protein, albumin, ALT, AST, ALP, total bilirubin), hsCRP
- CD4+ and CD8+ counts

An additional [REDACTED] of blood will be collected for study specific tests which include:

- Plasma HIV RNA (single copy assay)
- CA-US RNA on CD4+ T cells
- Cell associated HIV DNA (total and integrated) in CD4+ cells
- p24 expression
- PBMC and plasma storage
- Collection of plasma for measuring disulfiram pK levels
- Collection of serum for measuring vorinostat pK levels
- PAX gene tube for storage and future genetic studies

The total study specific blood volume collected for a participant over the 9 visits (approximately 6 months) will be 602.5 mL.

9. EFFECT ASSESSMENTS

9.1 PLASMA HIV RNA

HIV RNA in plasma will be measured by the AmpliPrep/COBAS®TaqMan® HIV-1 test version 2.0 (Roche Diagnostics) on three occasions and on all other visits, will be measured by a real-time PCR assay with single copy sensitivity as previously described².

9.2 TOLERABILITY

Tolerability will be assessed by systematically recording incidence and severity of adverse events. For each adverse event we will assess the causal association with study therapy (see section 10 for more details)

9.3 CELL-ASSOCIATED UNSPLICED HIV RNA

CA-US HIV RNA will be quantified using a semi-nested real time qPCR with a first round amplification of 15 cycles to ensure that the following second round amplification the assay was in the linear range between 1 to 46,000 input copies, as previously described by Pasternak et al ²⁴. Primers used for 1st and 2nd round amplified gag 25. HIV RNA copy numbers is standardized to cellular equivalents using an 18s RNA real time LUX PCR primer set (Invitrogen). PCR amplification of cDNA for CA-US RNA is performed in quadruplicate with a non-RT control included

9.4 P24 EXPRESSION

Will be measured by using an optimized HIV p24 digital immunoassay on the single-molecule-array platform using frozen PBMC.

9.5 CELL-ASSOCIATED TOTAL AND INTEGRATED HIV DNA

To measure total and integrated HIV DNA we will perform real time qPCR using primers and probes as previously described². The qPCR for HIV DNA will be performed in triplicate. To normalise for cell equivalents in the input DNA, a separate real-time qPCR assay will be used to quantify the CCR5 gene.

9.6 THE FREQUENCY OF INDUCIBLE VIRUS IN CD4+ T CELLS

We will use the recently developed Tat/rev Induced Limiting Dilution Assay (TILDA) to measure the frequency of cells with inducible multiply-spliced (MS) HIV RNA, as these transcripts are usually absent in latently infected cells but induced upon viral reactivation²⁶. Briefly, CD4+ T cells will be stimulated with phorbol myristate acetate (PMA) and ionomycin for 12hrs. Dilutions of the stimulated cells are then distributed in a 96 well plate and directly subjected to quantification of MS HIV RNA by qPCR. The frequency of positive cells is calculated using the maximum likelihood method and expressed as a frequency of cells with inducible MS HIV RNA per million CD4+ T-cells.

9.7 PLASMA LEVELS OF VORINOSTAT AND DISULFIRAM

Concentrations of vorinostat and disulfiram and its metabolites in plasma will be measured using liquid chromatography and mass spectrometry.

9.8 NEXT-GENERATION RNA SEQUENCING

We will perform next-generation RNA sequencing and bioinformatic analyses of gene expression activity in samples taken before, during and after study therapy. This will be done by extracting RNA including integrity control, stranded RNA library preparation and using Illumina sequencing with 100 bp single reads with enrichment for polyA tail mRNA.

During the expression analysis samples will undergo quality and adapter trimming, alignment, quantification and normalisation to generate output files that will be subject to bioinformatics analyses.

We will use these data to identify differentially expressed genes and affected gene pathways before study therapy, during treatment with disulfiram (day 0 – day 8), during treatment with disulfiram + vorinostat (day 8 – day 11) and at end of study (months after discontinuation of study therapy).

